Belimumab and placebo will be supplied as open-label vials and 3rd party unblinding will be employed. The study agent will be reconstituted and diluted by the unblinded site pharmacist or designee, independent of the study (person responsible for receiving and dispensing study agent). Separate monitors will be responsible for the clinical (blinded monitor) and study agent (unblinded monitor) aspects of the study.

If a medical emergency occurs and a decision regarding the subject's condition requires knowledge of the treatment assignment, the study blind may be broken for the specific subject. Whenever possible, the investigator should consult with the principal investigator of the study and data safety monitoring board prior to unblinding any subject. Any broken blind will be clearly justified and explained. The lead site and sponsor must be notified of any broken blind regardless of whether it was done for emergency or non-emergency reasons.

e. Concurrent Medications:

Corticosteroids: Patients that are on glucocorticoids at the time of screening will be required to be on a stable background dose for at least 2 weeks prior to screening (prednisone (or equivalent) dose \leq 15 mg daily).

The prednisone dose will remain stable until week 24 of the study, at which time a taper will be allowed at the discretion of the site investigator and principal investigator.

An increase in the dose of oral prednisone will be permitted, if clinically necessary, during the first 8 weeks after randomization without accounting it as a disease flare. In this case, the dose of prednisone must be tapered (to less than or equal to 25% of the baseline dose) by week 12. However, if the dose of prednisone cannot be tapered by week 12, the event will be considered as disease flare at that time.

Any increase of the prednisone dose after week 8 for IIM disease activity or the use of pulse steroids at any time during the study will be considered a disease flare. An increase of the prednisone dose at any time during the study for an event other than worsening of IIM disease activity will require the patient to return to the baseline dose of prednisone within 10 days, without accounting the event as a disease flare. Patients that are considered treatment failures will be allowed to remain in the study, in respective groups, at the discretion of the treating physician and PI.

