Immunosuppressive agents (IS): Enrolled patients could have had a history of treatment with any of the following IS agents: azathioprine, methotrexate, mycophenolate mofetil, leflunomide,

tacrolimus, cyclosporine, cyclophosphamide, Rituximab, or intravenous gamma globulin [IVIG]. Patients are not required to be on an IS agent at the time of enrollment.

During the enrollment and study period, the only allowed IS agents are: azathioprine, methotrexate, mycophenolate mofetil, tacrolimus, cyclosporine or intravenous gamma globulin [IVIG].

Patients that are on background immunosuppressive (IS) therapy at the time of screening will be required to be on a stable IS agent for \geq 2 months prior to screening (\geq 3 months for IVIG), and on a stable dose of IS agent for \geq 2 weeks prior to screening (except IVIG; no dose change allowed). Dose reduction due to poor tolerance of IS agent will be allowed on a case by case basis.

Therapeutic Agent	Treatment Duration prior to Screening \geq	Dose Increase prior to Screening \geq
Azathioprine	2 months	2 weeks
Methotrexate	2 months	2 weeks
Mycophenolate mofetil	2 months	2 weeks
Tacrolimus	2 months	2 weeks
Cyclosporine	2 months	2 weeks
IVIG	3 months	none

If a dose increase in IS agent or initiation of a new IS agent is clinically necessary during the randomization phase, this will be considered as a disease flare. The patient will be allowed to continue in their respective assigned group at the discretion of the treating physician and PI.

f. Medications and Therapies Prohibited for Concomitant Use:

a. Anti-B-cell therapy:

- i. Wash out of 5 therapeutic half-lives after prior B-cell therapy, or until pharmacodynamic effect would be minimal (e.g., 1 year following Rituximab)
 - IgG levels should be measured monthly in this situation
 - Benlysta should be discontinued in subjects with IgG levels <250 mg/dL associated with a severe or serious infection
- ii. If Rituximab use was medically indicated after the patient's enrolment to the clinical trial, the patient will no longer receive the investigational drug, but enhanced safety monitoring will be required.

b. Intravenous Cyclophosphamide

- i. 180 Days Prior to Belimumab
 - IgG levels should be measured monthly in this situation
 - Benlysta should be discontinued in subjects with IgG levels <250 mg/dL associated with a severe or serious infection

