2. Elevation of at least one muscle enzyme (creatinine kinase [CK]; myoglobin; alanine aminotransferase [ALT]; or aspartate aminotransferase [AST]) to a minimum level of 1.3 times the upper limit of normal.
3. Physician Global Assessment ≥ 2.0 cm using a visual analogue scale (VAS) 10.0 cm in length.
4. Patient Global Assessment ≥ 2.0 cm using a visual analogue scale (VAS) 10.0 cm in length.
5. Global extra muscular disease activity score ≥ 1.0 cm using a visual analogue scale (VAS) 10.0 cm in length. This score is based on the investigator's composite assessment of disease activity of the constitutional, cutaneous, skeletal, gastrointestinal, pulmonary and cardiac scales on the Myositis Disease Activity Assessment Tool (MDAAT).
6. HAQ disability index with a minimum value of 0.25.

The patient will be required to meet an MMT 8 score of $\leq 125/150$ as a major CSM criterion and at least 2 other CSM criteria to classify as an active disease.

In addition, for patients with ≥ 7 years of IIM, muscle biopsy or muscle MRI within 4 months prior to enrollment will be required to document active myositis to avoid enrolling patients with

significant index of damage/ muscle atrophy. This is not applicable to DM patients with a cutaneous VAS score of >3 cm on a 10 cm VAS scale (MDAAT).

Response rate: The response rate will be assessed by the percentage of patients meeting the definition of improvement (DOI). DOI is based on the definition of improvement developed by the International Myositis Assessment and Clinical Studies Group utilizing 6 core set measures.

DOI: DOI is defined as $\geq 20\%$ improvement in any 3 of the CSM, with no more than 2 CSM worsening by $\geq 25\%$ (excluding MMT)¹¹.

Definition of Worsening (DOW): Determination of worsening of the disease activity will be based on the definition of worsening (DOW) criteria developed by the International Myositis Assessment and Clinical Studies Group (IMACS) utilizing 6 core set measures¹¹:

1. worsening of Manual Muscle testing by $\geq 20\%$ and or Physician Global worsening of ≥ 2 cm on a 10 cm VAS or
2. Global extra muscular organ disease activity worsening by ≥ 2 cm on a 10 cm VAS on MDDAT, or
3. 3 of 6 CSM worse by $\geq 30\%$

Disease Flare: IIM Disease Flare is recorded when the patient:

1. reaches DOW;
2. new start or dose increase of corticosteroid or immunosuppressive agent for treatment of IIM after study week 8;

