3. an increased dose of corticosteroid before study week 8 and did not return to $<25\%$ above the baseline dose by week 12.

Endpoints:

1. **Primary Endpoint:**
 - a. Response rate at 40 weeks defined as percentage of patients meeting definition of improvement (DOI) in IIM patients treated with belimumab and standard therapy compared to the percentage of patients meeting DOI treated with placebo and standard therapy.
2. **Secondary Endpoints:**
 - a) Incidence of flares: flare rates during 40 weeks randomization period in patients with IIM treated with belimumab and patients treated with placebo and at week 64 in each group.
 - b) Time to achieve initial improvement defined as the time to reaching DOI.
 - c) Duration of improvement; quantified as the time from achieving improvement to the time of worsening or a disease flare. (Time from 1st DOI to 1st DOW or disease flare event). This will be based on the subset of subjects who achieve improvement.
 - d) Percent change in muscle enzyme levels (CPK and myoglobin) from baseline to week 40 and 64 in each respective group
 1. $<20\%$ reduction: no response
 2. 20-70% reduction: partial response
 3. $>70\%$ reduction: complete response
 - e) Percent change in manual muscle assessment (MMT-8) from baseline to week 40 and week 64 in each respective group.

- 1. <20% reduction: no response
- 2. 20-70% reduction: partial response
- 3. >70% reduction: complete response
- f) Percent change in prednisone dose from baseline to week 40 and week 64 in each respective group
- g) Proportion of subjects, among those on steroids at baseline, able to reduce the prednisone dose to ≤ 5 mg daily at week 40 and week 64 in each respective group.
- h) Flare rate in placebo group during the 40 week randomized treatment phase as compared to that group in the 20 week open label phase.
- i) Serious adverse event and adverse event rates
- j) Changes in B cell populations from baseline to week 40 and week 64
- k) Changes in autoantibody titers from baseline to week 40 and week 64
- l) Changes in immunoglobulin concentrations from baseline to week 40 and week 64

Inclusion Criteria:

Subjects enrolled in the study must meet the following inclusion criteria:

- 1) Adults ≥ 18 years of age
- 2) Have a diagnosis of:
 - a. definite or probable dermatomyositis (DM) by modified Bohan & Peter criteria or

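### The week-40 primary endpoint counts any patient meeting DOI as a responder, including one whose myositis therapy was escalated during the randomized phase

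*Combined protocol and SAP*

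**What the plan says.** **Escalation (Study Design, e. Concurrent Medications).** "Any increase of the prednisone dose after week 8 for IIM disease activity" is a disease flare, and so are pulse steroids at any time. A prednisone increase in the first 8 weeks is not a flare if it is tapered by week 12. The corticosteroid text ends: "Patients that are considered treatment failures will be allowed to remain in the study, in respective groups". That decision is left to the PI and the treating physician. For IS agents, "If a dose increase in IS agent or initiation of a new IS agent is clinically necessary during the randomization phase", that too is a flare, and "The patient will be allowed to continue in their respective assigned group at the discretion of the treating physician and PI".

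**Rituximab and cyclophosphamide (Study Design, f).** If either becomes medically indicated after enrolment, "the patient will no longer receive the investigational drug, but enhanced safety monitoring will be required". No outcome rule is attached.

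**Taper.** "The prednisone dose will remain stable until week 24 of the study, at which time a taper will be allowed at the discretion". The choice lies with the PI and the investigator at the site.

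**Endpoint.** Under Definitions, DOI requires at least 20% "improvement in any 3 of the CSM, with no more than 2 CSM worsening by" 25% or more (MMT excluded). It has no medication or flare component. The primary endpoint is "Response rate at 40 weeks defined as percentage of patients meeting definition of improvement (DOI"), compared between arms. Statistical Methods, item 1, tests that proportion by chi-square or Fisher's exact test. Flare appears only among the secondary endpoints.

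**Objective.** The first study objective compares response in refractory patients whose background treatment is stable.

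**The concern.** The plan treats escalation for myositis as a sign that the disease is not controlled, but the primary endpoint ignores it. Take a placebo patient who flares at week 16, starts a new IS agent and has improved on three core set measures by week 40. That patient is a flare in the secondary analysis and a responder in the primary one. The same holds for a belimumab patient who improves on a new agent, or on rituximab after belimumab was stopped.

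Scored this way, the endpoint measures improvement under whatever therapy was given, while the objective is stated for stable background therapy. More escalation on placebo would tend to narrow the difference. Escalated belimumab patients who then meet DOI would add to belimumab's count. With about eight responders expected in the whole trial under the planning rates, a few such patients can change the conclusion.

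**Working it through.** **1. The plan's own figure.** Inputs from Sample Size Considerations: 5% v 50%, two-sided alpha 0.05, 80% power, chi-square, no dropout. With mean rate p̄ = 0.275,

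n = [1.96·√(2p̄(1−p̄)) + 0.8416·√(p₁(1−p₁)+p₂(1−p₂))]² / (p₂−p₁)²
= [1.96·√0.39875 + 0.8416·√0.2975]² / 0.45² = 14.2, rounded up to 15 per arm.

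Formula power at 15 is 82%. The plan's 15 reproduces and is not in dispute.

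**2. The rules side by side.**

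| Event for myositis before week 40 | Plan's label | Stays in study? | Effect on week-40 DOI |
|---|---|---|---|
| Prednisone increase after week 8 | Flare | Permitted, at discretion | None |
| Pulse steroids, any time | Flare | Permitted, at discretion | None |
| New or increased IS agent | Flare | Permitted, at discretion | None |
| Rituximab or cyclophosphamide | None given in section f | Study drug stopped, monitoring continues | None |
| Early prednisone increase, tapered by week 12 | Not a flare | Yes | None |

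In every row, a patient who is assessed at week 40 and meets DOI is a responder.

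**3. What one or two patients do.** The planning rates give 15 × 0.50 = 7.5 and 15 × 0.05 = 0.75 expected responders. Uncorrected chi-square uses z = (difference/15)/√(p̄(1−p̄)·2/15). At 7 v 1, p̄ = 8/30 and z = 0.400/0.1615 = 2.48.

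| Belimumab v placebo responders of 15 | Chi-square p | Fisher p |
|---|---|---|
| 7 v 1 | 0.013 | 0.035 |
| 7 v 2 | 0.046 | 0.109 |
| 7 v 3 | 0.121 | 0.245 |
| 6 v 1 | 0.031 | 0.080 |
| 8 v 1 | 0.005 | 0.014 |
| 8 v 2 | 0.020 | 0.0502 |
| 8 v 3 | 0.058 | 0.128 |

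Expected responders per arm are 4.0 at 7 v 1, 4.5 at 7 v 2 and 3.5 at 6 v 1. All are below 5, where Fisher is the usual choice.

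**4. Illustrative power, on assumed rates.** Suppose 5% v 50% means response without escalation, a share r of non-responders is escalated, and a share d of those meets DOI. Then placebo = 0.05 + 0.95rd and belimumab = 0.50 + 0.50rd. The documents give neither r nor d. With r = 20%:

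| d | Both arms escalate | Formula power | Placebo only escalates (v 50%) |
|---|---|---|---|
| 0 (planned) | 5% v 50% | 82% | 82% |
| 25% | 9.8% v 52.5% | 74% | 69% |
| 50% | 14.5% v 55% | 66% | 55% |
| 83% | 20.8% v 58.3% | 56% | 38% |

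The 83% is the share meeting DOI in the rituximab trial cited in the sample size section. It is a high end only, since those patients received rituximab and not a steroid or IS adjustment. If 5% v 50% already means DOI as observed, there is no loss.

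**The case against.** The strongest reply is that the outcome is defined. DOI is specified, the endpoint counts it at week 40, the analysis is declared intention-to-treat, and analyses by treatment actually received are secondary. For a patient who stays and is assessed, these give one answer: DOI as observed, a treatment-policy approach that many statisticians would defend. That stands. A reader might infer that the primary outcome is undefined; the text does not support that. What remains is that the defined rule fits poorly with the stated objective and with the plan's own flare labels.

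Three other tempting readings also go too far.

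- *Every escalated patient is a treatment failure by protocol.* The term is not defined for this trial. Its link to escalation is inferred from its place in the corticosteroid text, and the IS text speaks only of flare.
- *The 5% placebo rate assumes escalated patients fail.* The sample size section does cite a trial in which all five placebo patients were treatment failures, but that is the cited trial's outcome and its definition is not given. The same section quotes a DOI rate and placebo effects of 0% to 40% at 12 weeks.
- *One patient decides the trial.* This is so under Fisher from 7 v 1. Under chi-square, the test used for sample size, one patient does not reverse it (7 v 2 gives 0.046, 6 v 1 gives 0.031). From 8 v 1, losing one belimumab responder leaves Fisher at 0.035. Some fragility of this kind comes with any binary endpoint at 15 per arm.

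**Conclusion.** The point holds as a mismatch between the primary scoring rule and the trial's stated question. The literal rule counts escalated patients who meet DOI as responders, while the plan calls steroid and IS escalation a flare and aims at response on a stable background.

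The size is bounded by the count examples: from 7 v 1, recoding one placebo patient takes Fisher's p from 0.035 to 0.109, and by chi-square two are needed (0.013 to 0.121). These need no assumed escalation rate, only that such patients occur. The power losses do depend on assumed rates and on reading 5% v 50% as response without escalation, so they are illustrations.

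A reader might infer a bias towards one arm or an inflated false-positive rate. The documents support neither. Direction depends on escalation rates they do not give, and if the drug has no effect and blinding is kept, either rule preserves type I error when fixed in advance.

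**What to change.** Before unblinding, amend the primary endpoint and Statistical Methods, item 1.

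1. **Primary scoring.** A patient is a week-40 non-responder if, before that visit and for myositis, any of these occurred:
   - a new start or increase of corticosteroid or IS agent after week 8, where a re-increase following a taper counts only if it exceeds the baseline dose;
   - an early prednisone increase not brought to less than 25% above baseline by week 12;
   - pulse steroids at any time;
   - rituximab or cyclophosphamide.

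   The permitted taper between weeks 8 and 12 does not count.
2. **Align two conflicts.** The week-12 prednisone limit is at most 25% of baseline in Concurrent Medications but under 25% above baseline in the flare definition; use the latter. State whether IS increases before week 8 count: Concurrent Medications treats them as flares, while the flare definition starts after week 8 and Statistical Methods permits standard-care dose adjustments in the first 8 weeks.
3. **Supportive analysis.** Report DOI as observed, regardless of escalation.
4. **Planning rates.** State which definition the 5% and 50% refer to.

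If the sponsor prefers DOI as observed as primary, it should say so, swap items 1 and 3, and justify the 5% on that basis.

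The cost is endpoint and analysis wording plus one extra analysis. Steroid and IS changes are already needed to define flares, so no new visits, data or patients are required. The downside is that response would partly reflect blinded clinicians' decisions to escalate, and rates may be lower in both arms.

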
1. For specific aim 1, the two treatment arms [B vs. P] will be compared with respect to the proportion of subjects who respond to treatment at 40 weeks (improvement according to definition), using either a chi-square test or Fisher’s exact test, as appropriate.
2. For specific aim 2, either a chi-square test or Fisher’s exact test, as appropriate, will be conducted to compare the proportion of subjects who had any flares during the 40-week randomized phase. For this analysis, each subject will be categorized at the end of 40 weeks as having had one or more flares or not having had any flares. In addition, we can also examine the total number of days that a subject had a specific flare during the course of the 40-week treatment, and compare the two treatment arms using the ‘Incidence density ratio’ method.
3. For specific aim 3, standard methods for survival analysis will be carried out. The Kaplan-Meier (KM) product limit method will be used to estimate overall “time-to-achieve (initial) response/improvement”. Ninety-five percent confidence intervals will be calculated using Greenwood’s formula for computing the standard error. Subjects who have not achieved improvement as of week 40 will be considered ‘censored’ for the event (event=improvement/response).
4. For specific aim 4, similar methods as indicated for specific aim 3 will be conducted. The analysis for this aim will be limited to the subset of subjects in each treatment arm who show improvement at anytime during the randomized phase of the trial. A subject who has not flared/worsened/relapsed as of week 40 will be considered ‘censored’ for the event (event=flare/relapse).
5. For specific aims 5, 6, 7, 9 and 10, each of the outcome variables of interest (uncensored continuous or categorical) will be analyzed separately, using a mixed model approach to repeated measures analysis of variance (MMRMANOVA) with the main effects of treatment arm (B vs. P), Disease type (PM vs DM), Disease Severity (Severe vs. Less Severe) and time (baseline vs. 40 weeks). If feasible, statistical interactions between

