From available trials in IIM, there is an observed placebo effect of 0%-40% at 12 weeks^{9,10} and 0% at 52 weeks⁹. These results demonstrate that the placebo response rate at 40 weeks can be very variable. One clinical study looking at rituximab in myositis was the first prospective, double-blind, randomized trial in myositis and the largest clinical trial ever performed in the inflammatory myopathies¹⁶. This trial employed a unique design; subjects were divided into two groups: early-start and delayed-start of rituximab. Overall, 83% of enrolled subjects (with severe refractory disease) met the DOI by the end of the trial, despite lack of statistical significance between groups. An alternate double-blind, placebo-controlled trial of etanercept (50 mg subcutaneously weekly for 52 weeks) where 16 subjects were randomized showed that: all 5 subjects receiving placebo were treatment failures (median time to treatment failure: 148 days)¹⁷. In contrast, 5 of 11 subjects in the etanercept arm were successfully weaned off prednisone; the median time to treatment failure in this group was 358 days ($p = 0.0002$). This data shows that for myositis trials, placebo response is often close to 0%. In order to achieve a clinically meaningful difference between study treatment arms, the response rate of the treatment group would need to be at least 50%.

We hypothesize (optimistically) the response rate at 40 weeks in the placebo arm to be 5%. We further assume that a magnitude of difference of 45% would be clinically meaningful (this corresponds to a 50% response rate in the Belimumab arm).

Based on the assumption that a difference of 45% in response rates at 40 weeks between Placebo and the investigational agent, Belimumab, would be clinically meaningful, then, a two group chi-square test ($\alpha=0.05$, two sided test) will yield 80% power to detect a difference between the Placebo arm week 40 response rate of 5% and a Belimumab-treated arm week 40 response rate of 50% (Odds ratio=19) when the sample size in each group is 15, assuming the dropout rate is 0%.

Table 1 below shows the sample size requirements for various pairs of (hypothesized) 40-week response rates and assumptions on what would be a clinically meaningful difference between treatment arms. Corresponding sample sizes are provided for the specified range of parameters. Calculations were based on a two-sided chi-square test to achieve 80% power ($\alpha=0.05$).

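### Follow-up after treatment failure is discretionary and a missing week-40 response has no scoring rule, so primary outcomes can be lost selectively among non-responders

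*Combined protocol and SAP*

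**What the plan says.** **Staying in the study.** Study Design, e. Concurrent Medications, ends its corticosteroid rules by saying that patients "considered treatment failures will be allowed to remain in the study, in respective groups, at the discretion of the treating physician and PI". Where an immunosuppressant is increased or newly started in the randomised phase, the event counts as a flare and "The patient will be allowed to continue in their respective assigned group at the discretion of the treating physician and PI". Treatment failure is not defined; the Definitions section covers improvement, worsening and flare only.

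**After study agent stops.** Under f. Medications and Therapies Prohibited for Concomitant Use, if rituximab or cyclophosphamide becomes necessary, "the patient will no longer receive the investigational drug, but enhanced safety monitoring will be required". Appendix C follows a liver stopping event with reporting, liver assessments and chemistry monitoring, and does not mention efficacy visits. Appendix A schedules the core set measures at week 40. It has no early-termination visit and does not say whether patients off drug must attend.

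**Analysis.** Statistical Methods, item 1, has the arms "compared with respect to the proportion of subjects who respond to treatment at 40 weeks", by chi-square or Fisher's exact test. It has no rule for a patient without a week-40 DOI; the only comparable rules are the censoring rules for the time-to-event aims. The analysis is called intention-to-treat but keeps only patients who received the first five infusions (weeks 0, 2, 4, 8 and 12). Sample Size Considerations gives the planned power "when the sample size in each group is 15, assuming the dropout rate is 0" per cent.

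**The concern.** The discretion in the corticosteroid rule covers remaining in the study, not just remaining on infusions. A patient who leaves under it has no week-40 core set measures and so no primary outcome. What prompts the decision is failure or flare, which is closely related to the outcome being measured. Any resulting missingness is therefore informative, and it falls on non-responders.

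The analysis does not close the gap. A patient who passes the five-infusion rule and leaves at week 20, say, is evaluable but has no DOI. The statistician must drop that patient from the denominator, score the patient as a non-responder, or impute, and the plan does not choose. With 30 patients, that choice could decide the primary result, and it could be made after unblinding.

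**Working it through.** **Inputs from Sample Size Considerations.** Placebo response: "We hypothesize (optimistically) the response rate at 40 weeks in the placebo arm to be 5" per cent. Belimumab: "this corresponds to a 50% response rate in the Belimumab arm". Alpha is 0.05, and the "two sided test) will yield 80% power to detect a difference". There are 15 patients per arm.

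**Reproducing the plan's figure.** Pooled-variance formula without continuity correction, with mean rate 0.275:

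n = [1.96·√(2·0.275·0.725) + 0.8416·√(0.05·0.95 + 0.50·0.50)]² / 0.45² = (1.238 + 0.459)² / 0.2025 = 14.2, rounded up to 15.

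The stated 15 per arm is reproduced. Approximate power at 15 is 82.3%. Enumerating all possible tables gives 87.0% for the uncorrected chi-square test and 73.6% for Fisher's test. These exact figures are the baseline below.

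**Effect of selective loss.** Let p be the true response rate and m the share of non-responders with no week-40 value. If only observed patients are analysed,

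observed rate = p / [p + (1 − p)(1 − m)].

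Every value of m is an assumption.

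*Equal loss, m = 0.40 in both arms:*
- Belimumab: 0.50 / (0.50 + 0.50·0.60) = 62.5%; expected missing 15·0.50·0.40 = 3.0.
- Placebo: 0.05 / (0.05 + 0.95·0.60) = 8.1%; expected missing 15·0.95·0.40 = 5.7.
- Difference: 54 points instead of 45.

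*Loss in one arm only, m = 0.40:* on belimumab, 62.5% v 5% (57.5 points); on placebo, 50% v 8.1% (42 points). The direction of bias depends on where the loss falls.

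**Rejection rates** (exact enumeration, 15 per arm, uncorrected chi-square, observed patients only):

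| Assumed loss of non-responders (placebo / belimumab) | Power, 5% v 50% | Type I error, 30% in both arms |
|---|---|---|
| none | 87.0% | 5.5% |
| 20% / 20% | 84.3% | 5.5% |
| 40% / 40% | 80.2% | 5.6% |
| 40% / 20% | 71.0% | not tabulated |
| 40% / 10% | 66.2% | 8.4% |

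In the last row, under no effect, the observed rates are 0.30 / (0.30 + 0.70·0.60) = 41.7% on placebo and 0.30 / (0.30 + 0.70·0.90) = 32.3% on belimumab. The 30% rate is illustrative.

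**How few patients matter.**
- 7/15 v 2/15 gives Fisher p = 0.109. If two belimumab non-responders have no week-40 value, 7/13 v 2/15 gives p = 0.042.
- In the other direction, 7/15 v 1/15 gives p = 0.035, but losing four placebo non-responders (7/15 v 1/11) gives p = 0.084.

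Uncorrected chi-square stays below 0.05 in all four tables (0.046, 0.022, 0.013, 0.040), so the reversal arises under Fisher's test. Expected responders per arm in the first table are 9/2 = 4.5. By the common convention of requiring at least 5 (the plan states no criterion), Fisher's test would be used.

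**The case against.** **The text permits staying.** Both discretion sentences are worded as permission to remain, and Statistical Methods says the protocol calls for patients to stay on their assignment. A reader might infer that failures will be removed; the documents do not say so. This stands. But permission is not a requirement to be assessed, and staying on assignment concerns treatment rather than measurement.

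**Safety monitoring is an addition.** The rituximab and cyclophosphamide rule adds monitoring and does not cancel the Appendix A visits. A reader might infer that every patient who stops drug gets safety follow-up only. For liver stops that rests on silence, and a liver stop is not in itself a poor myositis course. This stands too; what remains is that no sentence requires the efficacy visits.

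**Unequal loss is unsupported.** It is tempting to conclude that discretionary removal falls mainly on placebo, inflates its response rate, cuts power to 66–71% and raises type I error. Those figures need each placebo non-responder to be two to four times as likely to be lost as each belimumab non-responder. Investigator and patient are blinded in the randomised phase, and nothing in the documents supports such a ratio. More placebo patients would be lost under equal loss, simply because more are non-responders, yet the observed difference then widens. The plan also sends randomisation notifications to the PI, who shares the discretion, but it does not say that these reveal the assignment, so they do not establish unequal loss. Under Fisher's test, the type I error at 40% / 10% is only 5.0%.

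**Continued follow-up raises a question of its own.** A rescued patient may reach DOI because of the rescue. If 40% of placebo non-responders were rescued and 30% of those met DOI (both assumed), placebo response would be 5% + 95%·0.40·0.30 = 16.4%. This is a fair criticism of any remedy that only requires visits, so the scoring rule must cover rescue.

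**Conclusion.** The concern holds as a gap in follow-up and scoring: the plan as written permits outcome-dependent loss of the primary endpoint and does not say how to count those lost. It does not hold as a bias of known direction or size, because the documents give no loss rate other than 0%.

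Under an assumed equal 40% loss of non-responders, with only observed patients analysed, the apparent difference grows from 45 to 54 points, chi-square power falls from 87% to 80%, and type I error is essentially unchanged. The heavier figures apply only if loss per non-responder differs by arm, which is a sensitivity case. Independent of any assumed rate, results near the significance boundary can turn on two to four unassessed patients under Fisher's test. That is reason enough to settle the rule before unblinding.

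**What to change.** 1. In both discretion sentences of Concurrent Medications, separate remaining in follow-up from continuing study agent. State that all randomised patients who flare, are judged treatment failures, or stop study agent for any reason (including the rituximab and cyclophosphamide rules and Appendix C) stay in their randomised group and attend the scheduled Appendix A core-set visits through week 40, unless they withdraw consent. Define treatment failure or replace it with a defined term.
2. In Statistical Methods, item 1, state that a patient with no week-40 DOI counts as a non-responder. State in advance how a DOI reached after rescue therapy is scored, with a sensitivity analysis.
3. Apply both rules to all randomised patients, not only those with five infusions.

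Decisions on study agent and rescue are unchanged. If those missing are all non-responders, item 2 restores 50% v 5% with 15 per arm and 87% exact chi-square power. The cost is protocol wording and a few SAP sentences, since the visits already exist. Some off-drug patients would attend visits they might otherwise skip, and non-responder scoring is slightly conservative.
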